10.2 Secondary study parameter(s)

The secondary endpoint is analysed by comparing the effects of high-sodium on blood pressure increments during placebo and ertugliflozin treatment. An ANOVA analysis will be carried out to test significance between different conditions.

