2. OBJECTIVES

2.1 Primary objective:

1: To investigate the modifying effects of WHO-recommended sodium intake (90 mmol per day) vs. high sodium intake (targeted at 250 mmol per day) on the effect of ertugliflozin 15 mg daily, versus placebo, on 24-hour blood pressure in overweight/obese adults with type 2 diabetes.

2.2 Secondary objective:

To investigate the efficacy of ertugliflozin 15 mg daily, versus placebo, in overweight/obese adults with type 2 diabetes to reduce the hypertensive effects of a high-sodium diet (250 mmol per day) versus 24-hour blood pressure measurement during participant's normal diet (170 mmol/per day) obtained at screening visit.

[figure not shown]

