4.4 Sample size calculation

Based on previous studies in patients treated with SGLT2 inhibitors, we expect a change in systolic blood pressure of 6-8 mmHg during normal sodium intake (150 mmol/day) (6,7). Based on our hypothesis, this effect is increased on a low-sodium intake and reduced during high-sodium intake.

We expect a difference of 4 mmHg between the placebo-controlled effects of ertugliflozin on a low- versus high-sodium diet, with a conservative SD on this difference of 8 mmHg.

A total of 34 patients completing the study provide 80% power at a two-sided alpha of 0.05, to detect a 4 mmHg difference with the indicated SD of 8 mmHg. Drop-outs will be replaced.

Based on the RED study (7) and DAPASALT(6) study, the power needed to detect changes in GFR and hematocrit are of sufficient magnitude and therefore we expect sufficient power for these parameters as well. **We will include 34 individuals.**

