8.1.2 Secondary study parameters/endpoints (if applicable)

To investigate the efficacy of ertugliflozin 15 mg daily, versus placebo, in overweight/obese adults with type 2 diabetes to reduce the hypertensive effects of a high-sodium diet (250 mmol per day) versus 24-hour blood pressure measurement during participant's normal diet (170 mmol/per day) obtained at screening.

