After confirmation of eligibility during screening, a 24-hr blood pressure measurement as well 24-hr sodium excretion is measured prior to the dietary blocks as detailed below. This 24-hr sodium and blood pressure measurement will be crucial for hypothesis 2. Urine containers and 24-hr blood pressure meters are provided to the patient and collected after recording.

Screening	Day 0	Day 1 (offered at home of participants to reduce travel)
Medical history	X	
Physical examination	X	
Review of medication	X	
Office blood pressure	X	
Routine hematology and chemistry	X	
HbA1c	X	
Urinary dipstick	X	
Start 24-hr urine sodium collection	X	
Start 24-hr BP measurement	X	
Return 24-hr urine sodium collection		X
Return 24-hr BP measurement		X

Subsequently, 4 of the blocks of 20 days below are conducted in random order with differences in study medication (placebo versus ertugliflozin) and sodium diet (90 mmol/day versus 250 mmol/day). The washout is 4 weeks between the blocks. Please refer to the figure on page 11. Urine containers are provided to the patients.

A sodium diet is commenced (either aimed at 90 mmol/day or 250 mmol/day) and it is expected that after 10 days this is reached (+/- 20%, due to normal variation in sodium excretion). This will be assessed with two 24 hour urine collections. Subsequently, the diet is continued and treatment with the study medication commences. In the morning of day 9, 24-hour blood pressure recording starts. At the study visit at day 10 of treatment, endpoints are collected following an overnight fast of 10-hours at our clinical trial unit as indicated below. A flow chart of study activities is attached below.

Subject will arrive at Amsterdam UMC location AMC for multimetric MRI following an overnight fast. Subjects are then brought to Clinical Research Unit (CRU) location VUMC where the 24-hour urine collection is processed (in order to assess sodium

excretion and other variables of interest obtained from 24-hr urine collection). The 24-hour blood pressure recording is stopped. Two intravenous catheters will be placed in both forearms for blood sampling and for the administration of test-agents (e.g. iohexol and PAH). A total of 125 mL blood will be drawn during the day for this purpose. The renal protocol commences with measurement of GFR and effective renal plasma flow (ERPF) based on continuous infusion for 2.5.

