- 5) **Body-impedance analysis.** To measure body fat content we will use the tetrapolar Soft Tissue Analyzer® (STA, Akern, Florence, Italy), which can perform Bio-Impedance Analysis (BIA). This technique measures the resistance in the body tissues when a 50 kHz AC electrical current is given between four electrodes. Resistance can be measured by placing two electrodes on the dorsal hand and two on the foot at the unilateral side of the body (Lukaski & Bolonchuk, 1988). Extracellular water (ECW) as a percentage of total body water (TBW) and body cell mass (BCM) will be calculated independent of weight and height.
- 6) **ECG:** A 12-leads ECG will be made in the fasting resting state during screening in order to assess cardiac conduction parameters. Heart rate on the ECG will be defined as the mean rate of 10 R-R intervals. PQ-time, QRS-time and QT-time will be calculated, QT-time will be corrected for heart rate by using the Bazett formula (C. Bazett, 2006). The cardiac vector and ECG morphology will be assessed.
- 7) **Blood pressure and heart rate (office):** Blood pressure and heart rate will be measured using an automatic oscillometric device (Dinamap®, GE Healthcare) After an acclimatization period of >5 minutes, blood pressure will be measured three times at the non-dominant arm, with the subject in a semi-recumbent position, using an appropriate cuff-size. The mean of the last 2 measurements will be used as final value (Mengden et al., 2010; Pickering et al., 2005).
- 8) **GFR** is measured by steady-state plasma iothexol concentrations measured at T=120 and T=150 as done in our previous approved protocols.

9) **ERPF** is measured by steady-state plasma PAH concentrations measured at T=120 and T=150 as done in our previous approved protocols.

10) **Filtration fraction** (GFR/ERPF) and renal vascular resistance (ERPF/mean arterial pressure) are calculated.

12) **24-hour blood pressure** is derived from Mobil-O-graph devices (24 ambulatory blood pressure monitors, The Netherlands), which will be available at both sites.

Daytime systolic blood pressure (SBP), daytime diastolic blood pressure (DBP), nighttime SBP, daytime DBP and nocturnal dipping pattern (in mmHg) are recorded.

12) sodium sensitivity is calculated as following: changes in blood pressure due to the high-sodium diet versus diet at screening (estimated based on experience/previous trials at ~165-170 mmol/day) and the effect on this parameter by ertugliflozin versus placebo.

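### The secondary endpoint is labelled sodium sensitivity, but because the single screening blood pressure cancels, it estimates only ertugliflozin versus placebo on the high-sodium diet

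*Combined protocol and SAP*

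**What the plan says.** The secondary objective (section 2.2, repeated in the Summary and section 8.1.2) asks whether ertugliflozin, compared with placebo, is able "to reduce the hypertensive effects of a high-sodium diet (250 mmol per day) versus 24-hour blood pressure measurement" on the usual diet. Section 2.2 gives the reference as "24-hour blood pressure measurement during participant's normal diet (170 mmol/per day) obtained at screening visit".

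Section 8.3 (the second of two items numbered 12) defines sodium sensitivity as "changes in blood pressure due to the high-sodium diet versus diet at screening", "and the effect on this parameter by ertugliflozin versus placebo". The screening part of section 8.3 calls this hypothesis 2, the effect of ertugliflozin on sodium sensitivity, and treats the screening recording as essential to it.

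The reference is taken once: "a 24-hr blood pressure measurement as well 24-hr sodium excretion is measured prior to the dietary blocks". SGLT2 inhibitor users are excluded (section 4.3), so this recording is off drug. The block schedule in section 8.3 has no usual-diet BP on ertugliflozin or on placebo.

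For the analysis, section 10.2 says "The secondary endpoint is analysed by comparing the effects of high-sodium on blood pressure increments during placebo and ertugliflozin treatment", and then "An ANOVA analysis will be carried out to test significance between different conditions". It gives no formula for the contrast and does not mention the low-sodium periods.

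On the expected drug effect, section 4.4 gives 6-8 mmHg systolic at normal intake and adds that "this effect is increased on a low-sodium intake and reduced during high-sodium intake", with a 4 mmHg difference between the two diets.

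**The concern.** An effect on sodium sensitivity means that the BP change caused by a change in sodium intake differs between drug and placebo. To see that, BP is needed at two sodium intakes on each treatment. The secondary endpoint has the second intake (usual diet) only off drug, and uses the same value for both treatments. The reference therefore cannot separate a drug that blunts the response to sodium from one that lowers BP regardless of sodium.

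This is the trial's only secondary objective, and it carries a mechanistic claim. A general antihypertensive effect, which the plan expects, could be reported as reduced sodium sensitivity. The result could also conflict with the primary analysis. If the drug works better on low sodium, as section 4.4 hypothesises, BP rises more with sodium on ertugliflozin than on placebo. The secondary could nevertheless be reported as showing the opposite.

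**Working it through.** **Notation.** H = high sodium, L = low sodium, S = screening; E = ertugliflozin, P = placebo.

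**1. The plan's own figure.** Inputs from section 4.4: difference 4 mmHg, SD of that difference 8 mmHg, two-sided alpha 0.05, 80% power. Section 10 states a paired design. A paired t-test with n = 34 has noncentrality 4 / (8/√34) = 2.92 and power 80.8%; 34 is the smallest n reaching 80%. The stated sample size reproduces. No power is stated for the secondary endpoint.

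**2. The secondary contrast.** From the definition in section 8.3:

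(H_E − S) − (H_P − S) = H_E − H_P

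The cancellation is exact for every participant with both high-sodium periods, which the per-protocol completer set in section 10.1 ensures. If the carryover rule in section 10.1 left only period 1, S would cancel in expectation through randomisation. Adding screening BP as a covariate or as an extra ANOVA condition does not change what the E-versus-P contrast estimates.

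**3. The contrast that measures a change in sodium sensitivity across the randomised diets.**

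(H_E − L_E) − (H_P − L_P) = (H_E − H_P) − (L_E − L_P)

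This is the primary diet-by-drug interaction, rearranged.

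**4. SD of H_E − H_P.** This is not stated, so it is an assumption. If the drug effects on the two diets have equal SD s and within-person correlation r, then 8² = 2s²(1 − r). With r = 0, s = 8/√2 = 5.66; with r = 0.5, s = 8. Values of 10 and 12 correspond to r = 1 − 64/200 = 0.68 and r = 1 − 64/288 = 0.78. All four are shown.

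**5. Probability of a significant result at n = 34** (paired t-test, two-sided 0.05):

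| Drug effect on high sodium | SD 5.66 | SD 8 | SD 10 | SD 12 |
|---|---|---|---|---|
| 6 mmHg | >99.9% | 98.9% | 92.4% | 80.8% |
| 5 mmHg | 99.9% | 94.3% | 80.8% | 65.5% |

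**6. Equal effect at every intake.** Take 6 mmHg, the low end of the plan's 6-8 mmHg, on both diets. The true effect on sodium sensitivity is 6 − 6 = 0, and the first row gives the chance of a positive secondary. A simulation of 20,000 trials (within-condition SD 4, so that the interaction SD is 8; between-person SD 10) gave a significant reduction on the secondary in 100% of trials. The interaction test rejected in 5.0% of the same trials.

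**7. The plan's own hypothesis.** As an illustration of the 4 mmHg difference, let the drug lower BP by 9 mmHg on low and 5 mmHg on high sodium. The rise from low to high on drug minus that on placebo is −5 − (−9) = +4 mmHg, so sodium sensitivity increases. The secondary estimate is −5 mmHg, and the second row applies. In simulation (SD 5.66) it was a significant reduction in 99.8% of trials. From usual to high intake the direction is the same: with 7 mmHg at usual intake (the middle of 6-8) and 5 on high, the rise on drug is 7 − 5 = 2 mmHg larger.

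**8. No BP effect at all.** The same simulation with zero drug effect gave a significant reduction in 2.5% of trials, the nominal one-sided rate.

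**The case against.** - **The formal objective can be read more narrowly.** Sections 2.2 and 8.1.2 may mean only that the drug offsets BP on high sodium. H_E − H_P answers that with a valid randomised comparison. This stands. The mismatch lies in the sodium-sensitivity label in section 8.3, and the fix is a matter of naming.
- **Section 10.2 specifies no contrast.** This also stands. The cancelling contrast is inferred from sections 2.2 and 8.3. It is the natural reading, and nothing elsewhere supplies another.
- **The study calls itself hypothesis-generating (section 10.1).** That argument concerns multiplicity. It does not make a contrast measure the quantity it is named after.
- **High minus low is a different question.** It spans 90 to 250 mmol/day, not about 170 to 250. This is true and should be stated. Keeping the usual-diet question would need a usual-diet BP on each treatment, which the schedule lacks.

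A reader might infer more than the documents support:

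- **That any drug without an effect on sodium sensitivity would be declared to reduce it.** This needs a drug that lowers BP on high sodium, and even then it is a probability. With no BP effect the rate is about 2.5%.
- **That the non-randomised, always-first screening value biases the drug comparison.** It cannot, because it cancels. It affects only the increments within each treatment. The reference is also not wholly uncontrolled: 24-hour sodium is measured at screening, and baseline intake is capped below 200 mmol/day (section 4.2).
- **That the trial cannot address sodium sensitivity.** The primary interaction already does, over the randomised diets.

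**Conclusion.** The point holds as a mislabelled secondary estimand. As defined, the endpoint is the ertugliflozin-versus-placebo difference in 24-hour BP on high sodium. It cannot support a conclusion about sodium sensitivity.

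If BP falls by 6 mmHg at every intake, the chance of a positive secondary despite a zero effect on sodium sensitivity runs from 80.8% to above 99.9% over the assumed SDs. For the illustrative 5 mmHg effect on high sodium under the plan's hypothesis, it runs from 65.5% to 99.9%, while the true change is a 4 mmHg larger rise on drug. These figures assume 34 completers, a paired t-test, the natural reading of section 10.2 and an SD that the plan does not give. The algebra depends neither on the SD nor on the 9/5 split.

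The primary analysis and the sample size of 34 are unaffected. This should be fixed before the data are reported, but it does not threaten the trial's main result.

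**What to change.** 1. In the Summary and sections 2.2, 8.1.2, 8.3 (the hypothesis 2 wording and the sodium-sensitivity item) and 10.2, rename the secondary endpoint as the effect of ertugliflozin versus placebo on 24-hour BP on the high-sodium diet. Drop the sodium-sensitivity claim from it.
2. In section 10.2, write the contrast out as H_E − H_P.
3. Draw any conclusion on sodium sensitivity from (H_E − L_E) − (H_P − L_P). State that this equals the primary interaction, is not a separate test, and covers 90 to 250 rather than 170 to 250 mmol/day.
4. Report high-sodium placebo minus screening descriptively, noting that this increment is non-randomised and confounded with time.

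The cost is wording only, with no new measurements or participants. The trial loses one apparently separate claim.

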10.3 Other study parameters

All exploratory variables are analysed as described under 10.1. For exploratory parameters, no correction for multiple testing will be conducted and the exploratory nature of the data will be stressed when the data are reported in a manuscript as our group has done previously.

10.4 Interim analysis (if applicable)

No interim analysis will be performed

11. ETHICAL CONSIDERATIONS

11.1 Regulation statement

The study will be conducted according to the principles of the Declaration of Helsinki (Fortaleza, 2013), in accordance with the Medical Research Involving Human Subjects Act (WMO), and in accordance to the European Clinical Trial Regulation (ECTR). The investigator will ensure that all aspects of the institutional ERB review are conducted in accordance with current institutional, local and national regulations.

11.2 Recruitment and consent

Patients will be enrolled to the trial from centers in the Netherlands (1 center) and the United States (1 center). Potential participants will be approached through (a) the diabetescenter database, which has registered participants that have given consent to be approached for new studies by their informed consent form of a former stud, (b) adds online or in local newspapers, or (c) through their own physician.

- (a) Former participants of former studies, that gave their consent to be approached for new studies, can be contacted by the research physician. In case of a positive response, the participant information letter will be sent out. After a minimum of a week, in which the possible participant can read the information and formulate questions, the research physician will contact the possible participant again and answer any questions. If the possible participant wishes to participate, an appointment will be made for the screening visit. During this visit there again is room for explanation of the study and questions. Then, before the commencement of any study procedures, the informed consent form will be signed in twofold by the participant and the research physician.
- (b) People who have read the add and have interest in participation of the study can contact the research physician by mail or by phone. After the initial contact has been made, the procedure is similar to the procedure described above. The research physician will explain the details of the study and the PIF will be sent. After at least a week, there will be a second contact moment and room for questions. In case of a positive response, the possible participant will be invited to the hospital for a screening visit. During this visit there again is room for explanation of the study and questions. Then, before the commencement of any study procedures, the informed consent form will be signed in twofold by the participant and the research physician.
- (c) A doctor that is familiar with current study, can ask his/her own patients if they have interest in participation in the study and if the research physician can contact them. In case of a positive response, the procedure is similar to the procedure described above. The research physician will contact the possible participant and explain the details of the study and the PIF will be sent. After at least a week, there will be a second contact moment and room for questions. If the possible participant wishes to participate he/she will be invited to the hospital for a screening visit. During this visit there again is room for explanation of the study and questions. Then, before the commencement of any study procedures, the informed consent form will be signed in twofold by the

participant and the research physician.

11.3 Benefits and risks assessment, group relatedness

All participants will receive ertugliflozin, an SGLT-2 inhibitor which is approved for blood-glucose lowering treatment in T2DM patients. Based on currently available data from thousands of patient years, the drug has shown to be safe. In addition to glucose-lowering, SGLT-2 inhibitors have other beneficial effects, by inducing a decrease in blood pressure and body weight for instance. Clinically, SGLT2 inhibitors prevent kidney function decline, hospitalization for heart failure and cardiovascular events after longer-term use.

SGLT2 inhibitors have side effects. The most common side effect are genital mycotic infections, which can be treated with a topical antimycotic crème. Other side effects include polyuria, frequent voiding and nycturia.

As in all drug intervention trials, in this study, we will closely monitor patients for adverse drug and study events. Participants can contact the research staff 24 hours a day. It should be noted that most of these side effects rarely occur in such a short treatment duration as in the current study. There is no risk of a short-term change in sodium diet on long-term health outcomes. In addition, effects of high-sodium diet [e.g. on blood pressure] are closely monitored.

11.4 Compensation for injury

The sponsor/investigator has a liability insurance which is in accordance with article 7 of the WMO. The sponsor (also) has an insurance which is in accordance with the legal requirements in the Netherlands (Article 7 WMO). This insurance provides cover for damage to research subjects through injury or death caused by the study.

The insurance applies to the damage that becomes apparent during the study or within 4 years after the end of the study.

11.5 Incentives

Patients will receive restitution of all costs for transportation and a honorarium of 500 euro for participating. In case of premature termination, the reimbursement of the participant will be based on the actual duration of participation in proportion to the planned duration of participation.

12. ADMINISTRATIVE ASPECTS, MONITORING AND PUBLICATION

12.1 Handling and storage of data and documents

In accordance with the Dutch law 'Algemene verordening gegevensbescherming' (AVG; General Privacy Law) and GCP all patient data will be handled confidentially. Therefore, all participants at Vumc will get a study code ('DES-0xx'). The code list, with both identifier data and study number, will be stored securely on the server of the VUMC, protected by passwords only known by the responsible research physicians and principal investigator.

All subject data will be recorded on printed CRF by the local investigator and/or personnel that is instructed in performing these administrative tasks and study procedures. In the latter case, data will always be reviewed by the investigator. All subject related data will be stored for the legally required period of 25 years. With regard to the body material, data will be stored for a maximum of 5 years and will only be used for the research questions within the scope of current research. Subject data, both encoded (e.g. CRFs) or not (e.g. source documents), will always be stored securely, in a locked cabinet in the Diabetes Center VUMC or on password secured computers.

For the site in Colorado, the same principles are maintained as indicated here. Data from the US site will be sent to Amsterdam UMC, in an anonymized matter (using a study code DES-1xx). This has been described in the study contract between sites. Vice versa, data will not be send from the Dutch site to the US.

Monitoring and Quality Assurance

The study will be monitored by an appointed monitor of the VU ethical review board. The monitor will conduct (a frequency of) quality assessments in accordance to the guidelines of the institution. Monitoring at Colorado University is carried along the same principles with a local monitor.

